#### **10.1.2 Serious Adverse Events**

A summary of incidence rates (frequencies and percentages) of SAEs by treatment group, SOC, and preferred term will be prepared for the Safety population. A data listing of SAEs will also be provided, displaying details of the event(s) captured on the CRF.

#### **10.1.3 Deaths**

A listing of deaths will also be provided for the Safety Population.

### **10.2 Clinical Laboratory Evaluations**

Laboratory data include analyses for Chemistry and Hematology will be summarized by treatment and visit for the Safety Population. Descriptive summaries of actual values and changes from baseline will be presented by study visit and each treatment group. 95% confidence intervals will be presented for change from baseline for each visit and last on-treatment assessment. ET data will be mapped to the closest visit window as described in

**Section 7.1.2**, but will typically only be used if a valid assessment was not collected then (scheduled visits will usually be closer to the target visit day and will take precedence if the ET and scheduled visit are equidistant to the target visit day).

Laboratory values will be displayed in the data listings and those that are outside the normal range (“H” or “L”) will be flagged, along with corresponding normal ranges. Values pre-defined as potentially clinically significant (“HH” or “LL”) will also be flagged. For each laboratory analysis, shifts in assessments of abnormality from baseline to each scheduled time point will be presented in shift tables.

A by-participant listing of all clinical laboratory data will also be provided.

### **10.3 Columbia Suicide Severity Rating Scale (C-SSRS)**

The C-SSRS is an instrument that measures suicidal ideation and behavior. Items measuring suicidal ideation and suicidal behavior are displayed in the table below. Frequency counts of yes/no responses to items below and whether any suicidal ideation or behavior is present will be summarized as described below.

The overall number of participants with lifetime and/or recent (past 6 months) suicidal ideation (by item, e.g., Ideation Types 1-5), and lifetime and/or recent (past 12 months) suicidal behavior (by item; e.g., Preparatory Act, Aborted Attempt, Interrupted Attempt, Actual Attempt and Completed Suicide), or non-suicidal self-injurious behavior at the screening and baseline visit will be summarized by visit and treatment group.

Additionally, the overall number of participants with any suicidal ideation or behavior (by type and in total) or self-injurious behavior while on-treatment will be provided by treatment group. For ideation, participants will only be counted once at each visit and/or time frame at the worst case response for ideation type (1-5), where 1 is the least severe and 5 is the most severe type of ideation.

Category	Items
A) Suicidal Ideation	(1) Type 1: Wish to be dead (2) Type 2: Non-specific active suicidal thoughts (3) Type 3: Active suicidal ideation with any methods (not plan) without intent to act (4) Type 4: Active suicidal ideation with any some intent to act, without specific plan (5) Type 5: Active suicidal ideation with specific plan and intent
B) Suicidal Behavior	(1) Preparatory acts or behavior (2) Aborted attempt (3) Interrupted attempt (4) Actual attempt (5) Completed suicide Suicidal Behavior present (composite of items 1-5) Non-Suicidal Self-Injurious Behavior

Suicidal intensity of ideation will be calculated by tallying up the five intensity items to

create a total score ranging 0-25. If a participant does not have any suicidal ideation, a score of 0 will be given. Separate tables will be created for the entire Safety Population as well as the population comprising only participants exhibiting any suicidal ideation. Suicidal intensity of ideation total score will be summarized using descriptive statistics by treatment group.

A data listing of C-SSRS results will include only participants with suicidal ideation, suicidal behavior, or self-injurious behavior without suicidal intent. For participants with suicidal ideation, suicidal behavior, or self-injurious behavior without suicidal intent at any time, data from all visits are displayed.

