Adverse events will be coded using the Medical Dictionary for Regulatory Activities (MedDRA) version in use at the start of the study and will be summarized overall and by preferred term and system organ class. Adverse events will also be summarized by severity and relationship to study drug. Serious AEs and AEs leading to discontinuation of study drug will also be summarized. Actual values and changes from baseline for clinical laboratory test results, vital sign measurements, MADRS scores, and CSFQ-14 scores will be summarized at endpoint using descriptive statistics (n, mean, SD, median, minimum, and maximum).

The number of patients with screening, baseline and treatment-emergent suicidal ideation and/or behavior, based on the C-SSRS will be summarized by treatment group.

Interim Analysis

An interim analysis will be performed once approximately 50% of the planned patients have enrolled and those patients have either completed or discontinued the study. The purpose of the interim will be to potentially increase the sample size to maintain statistical power conditioned on the results of the first 50% of patients; or stop the study for futility if the conditional power is sufficiently low. The study team will only be informed of the recommendation to maintain the original sample size,

increase the sample size (by a fixed, pre-specified amount) or discontinue the study (at which point unblinding would occur).

For the primary and key secondary outcomes, the results from before and after the interim will be combined with Cui, Hung, Wang (CHW) methodology ([Cui, 1999](#)). Full details of the interim analysis procedure and steps to maintain treatment blinding of the study team will be described in the SAP and the IDMC Charter and finalized prior to execution of the interim analysis.

Sample Size Estimation

The study is planned to enroll approximately 250 patients total in a 1:1 randomization, that is, 125 patients in each of the TNX-102 SL 5.6 mg and placebo arms. [REDACTED]

[REDACTED]

Pharmacogenomic Analyses

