7.3.4. Safety

Safety will be assessed by:

- Adverse events (AE) and serious AEs (SAEs) throughout the entire duration of the study, including detailed assessment of AEs involving the oral cavity
- Changes from baseline in clinical laboratory test results
- Changes from baseline in vital signs and weight
- Change from baseline in MADRS score
- Changes from baseline indicative of increased suicidal ideation or behavior as assessed by the Columbia Suicide Severity Rating Scale (C-SSRS)
- Changes from baseline in patient-rated Changes in Sexual Functioning Questionnaire Short-Form (CSFQ-14) in males and in females, described separately

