8.3. Exclusion Criteria

Eligible patients who meet any of the following criteria during the screening period should be excluded from the study:

1. Current or ongoing exposure to the trauma that resulted in the PTSD.
2. Increased risk of suicide on the basis of the Investigator's judgment and/or the results of the Mini International Neuropsychiatric Interview, Version 7.0.2 (M.I.N.I. 7.0.2) conducted at Screening and the Columbia Suicide Severity Rating Scale (C-SSRS) conducted at Screening and/or Baseline and Item 10 of the Montgomery-Åsberg Depression Rating Scale (MADRS) at Screening and/or Baseline. Any of the following will be exclusionary:
 - a. High suicidality based on a M.I.N.I. Module B score ≥ 17 (Screening); or,
 - b. Patient answers YES to either M.I.N.I. question B10 or B11 (Screening); or,
 - c. Patient meets criteria for CURRENT Suicidal Behavior Disorder on the M.I.N.I (Screening); or,
 - d. C-SSRS Type 4 or Type 5 ideation within 6 months of Screening or at the Baseline visit; or,
 - e. Any suicidal behavior in the past 12 months as identified by the C-SSRS at Screening or Baseline.
 - f. A score of > 4 on Item 10 of the MADRS at Screening or Baseline.
3. Increased risk of suicide, based on the Investigator's judgment that is of a severity that is not appropriate for outpatient management, or that warrants additional therapy excluded by the protocol.
4. Significant (e.g., moderate or severe) comorbid traumatic brain injury (TBI) by history. Based on past history and Investigator's judgment, patients with mild TBI are eligible.
5. Severe depression suggested by a Screening (Visit 1) MADRS score > 26 . Patients with a Screening MADRS score of ≥ 26 may be randomized upon Medical Monitor approval, based on a review of all Screening rating scales and the patient's psychiatric/medical history.
6. Clinically significant laboratory abnormalities based on screening laboratory tests and/or medical history in the Investigator's opinion, including a Thyroid Stimulating Hormone (TSH) level > 1.5 times the upper limit of normal and aspartate aminotransferase (AST) and/or alanine aminotransferase (ALT) > 3 times the upper limit of normal (if persistent upon repeat). Patients with treated thyroid conditions and TSH levels ≤ 1.5 times the upper limit of normal will be eligible to participate in the study.

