13.5. Safety Analyses

Safety will be assessed by:

- Adverse events and serious AEs throughout the entire duration of the study, including assessment of AEs involving the oral cavity
- Changes from baseline in clinical laboratory test results
- Changes from baseline in vital signs and weight
- Changes from baseline indicative of increased suicidal ideation or behavior as assessed by the C-SSRS
- Changes from baseline in MADRS scores
- Changes from baseline in patient-rated sexual function as assessed by the CSFQ-14 in males and in females, described separately

Adverse events will be coded using the latest version of MedDRA and will be summarized overall and by preferred term and system organ class. Adverse events will also be summarized by severity and relationship to study drug. Serious AEs and AEs leading to discontinuation of study drug will also be summarized. Actual values and changes from Baseline for clinical laboratory test results, MADRS scores, CSFQ-14 scores, and vital sign measurements will be summarized at endpoint using descriptive statistics (n, mean, SD, median, minimum, and maximum).

The number of patients with suicidal behaviors, ideations and acts based on the C-SSRS will be tabulated by treatment group and listed.

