### **2.2.3 Safety Endpoints**

Safety will be assessed by:

- Adverse events (AE) and serious AEs (SAEs) throughout the entire duration of the study, including detailed assessment of AEs involving the oral cavity.
- Changes from baseline in clinical laboratory test results.
- Changes from baseline in vital signs and weight.
- Change from baseline in MADRS score.
- Changes from baseline in suicidal ideation or behavior as reported on the Columbia Suicide Severity Rating Scale (C-SSRS).
- Changes from baseline in participant-rated CSFQ-14.

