### 7.3 Safety Assessments

Safety will be assessed by:

- AEs and SAEs throughout the entire duration of the study, including detailed assessment of AEs involving the oral cavity.
- Changes from baseline in clinical laboratory test results.
- Changes from baseline in vital signs and weight.
- Change from baseline in MADRS (see [Section 7.2.4](#)).
- Changes from baseline indicative of increased suicidal ideation or behavior as assessed by the C-SSRS.
- Changes from baseline in participant-rated CSFQ-14.

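### SAP 10.3 counts any suicidal ideation on treatment, so no planned table gives the number of patients per arm whose Type 1-3 ideation was new or worse than at baseline

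*SAP*

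**What the plan says.** **Endpoint.** SAP 7.3 lists as a safety measure "Changes from baseline indicative of increased suicidal ideation or behavior as assessed by the C-SSRS". Protocol 7.3.4 and the opening list of Protocol 13.5 say the same in substance. SAP 2.2.3 also defines the measure as change from baseline.

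**Promised summary.** The protocol synopsis says: "The number of patients with screening, baseline and treatment-emergent suicidal ideation and/or behavior, based on the C-SSRS will be summarized by treatment group". The closing sentence of Protocol 13.5 is looser: "The number of patients with suicidal behaviors, ideations and acts based on the C-SSRS will be tabulated by treatment group and listed".

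**Planned tables.** SAP 10.3 gives screening and baseline counts by arm, and then "the overall number of participants with any suicidal ideation or behavior (by type and in total) or self-injurious behavior while on-treatment". For ideation, each patient is counted once per visit or time frame, at the worst type from 1 to 5. The section adds an ideation intensity score (0-25) summarized by arm, and a listing of all visits for patients with any event. It defines no treatment-emergent or worsening category and has no shift table. SAP 10.2 does specify shift tables for laboratory data.

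**Entry.** Protocol 8.3 item 2 excludes "C-SSRS Type 4 or Type 5 ideation within 6 months of Screening or at the Baseline visit" and any suicidal behavior in the past 12 months, along with several other suicidality criteria. None of them removes Types 1-3 by type. Protocol 7.1 and 11.3.3 foresee scores of 2 or 3 from Screening onward.

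**Declared departures.** SAP 12 states that there are none from the protocol.

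**The concern.** A change-from-baseline endpoint needs each patient's on-treatment status to be set against that patient's own status before treatment. The SAP's worst-case rule selects a type within a visit or time frame and stops there. A patient who enters with Type 2 ideation and stays at Type 2 is counted on treatment exactly like a patient with new Type 2 ideation. A move from Type 1 to Type 3 appears in the Type 3 row with nothing to mark it as worsening.

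At stake is how clearly the two arms can be compared on suicidality in a PTSD population where some ideation at entry is allowed. If many patients carry ideation into the trial, a drug-related increase in Types 1-3 would look proportionally smaller in the planned table than it is. The reference for an emergent count is also left open. The general baseline rule in SAP 7.1 points to Visit 2, where the form covers the time since the last visit. The Screening form covers lifetime and the past 6 months. If that choice is made only after unblinding, the results could influence it.

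**Working it through.** **Step 1. Set each place beside what it delivers.**

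| Place | What it gives | By-arm count of patients who worsened? |
|---|---|---|
| Protocol 7.3.4, 13.5 (list); SAP 2.2.3, 7.3 | Endpoint: change from baseline | Required in substance |
| Protocol synopsis | Screening, baseline and treatment-emergent counts | Promised, term not defined |
| Protocol 13.5 (closing sentence) | Tabulation by arm and listing | Not mentioned |
| SAP 10.3, counts | Screening/baseline counts; any event on treatment | No |
| SAP 10.3, intensity score | Descriptive statistics by arm; change from baseline possible under the general rule in SAP 10 | No, summary statistics of a score |
| SAP 10.3, listing | All visits, patient by patient | No, not a summary by arm |
| SAP 10.1 | Adverse event tables by arm | Only events that were recorded as adverse events |

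Two separate counts cannot stand in for the missing one. Equal numbers at baseline and on treatment fit an arm in which nobody changed. They fit equally well an arm in which everyone with ideation lost it and the same number of other patients gained it.

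**Step 2. Find the affected rows.** Recent Type 4-5 ideation (6 months) and suicidal behavior (12 months) are excluded at entry. An on-treatment case in those rows is therefore in effect new. Only the Type 1-3 rows and the ideation totals mix unchanged with new or worse.

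**Step 3. Illustrate the size.** The plan has no C-SSRS rate to reproduce, so every rate here is an assumption. Let b be the share entering with Type 1-3 ideation, p the share of these who report ideation again on treatment (the same in both arms), and e the rate of new ideation among the rest: 0.05 on placebo and 0.10 on drug, a true relative risk of 2.0.

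Any-on-treatment rate = b × p + (1 − b) × e

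| b | p | Placebo | Drug | Ratio | Difference (points) |
|---|---|---|---|---|---|
| 0.15 | 0.6 | 13.25% | 17.50% | 1.32 | 4.25 |
| 0.15 | 0.8 | 16.25% | 20.50% | 1.26 | 4.25 |
| 0.25 | 0.6 | 18.75% | 22.50% | 1.20 | 3.75 |
| 0.25 | 0.8 | 23.75% | 27.50% | 1.16 | 3.75 |
| 0.35 | 0.6 | 24.25% | 27.50% | 1.13 | 3.25 |
| 0.35 | 0.8 | 31.25% | 34.50% | 1.10 | 3.25 |

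For example, at b = 0.25 and p = 0.8, placebo is 0.20 + 0.75 × 0.05 = 0.2375 and drug is 0.20 + 0.75 × 0.10 = 0.275. The ratio falls from 2.0 to between 1.10 and 1.32. The absolute difference falls only from 5 points to 3.25-4.25. That fall is the factor (1 − b), because the new cases are now divided by the whole arm. The carry-over term b × p adds equally to both arms: it shrinks the ratio and adds noise.

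**Step 4. Vary the model.** Let e now be the rate of new or worsened ideation in the whole arm, and r the share of patients with entry ideation who still report it without worsening.

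Any-on-treatment rate = e + (1 − e) × b × r, with b from 0.10 to 0.30 and r from 0.5 to 0.8.

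- For 4% v 10% (ratio 2.5), the planned count runs from 8.8% v 14.5% (ratio 1.65) to 27.0% v 31.6% (ratio 1.17).
- For 5% v 15% (ratio 3.0), it runs from 9.8% v 19.3% (ratio 1.97) to 27.8% v 35.4% (ratio 1.27).
- Patients who did not worsen make up 22-68% of those counted on drug and 49-85% of those counted on placebo.

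The direction is the same under both models. The size depends on rates that nobody can read from these documents.

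**The case against.** The strongest reply is that worsening is already captured elsewhere. Protocol 11.3.3 has a post-baseline score of 2 or 3 recorded as an adverse event if it is a significant change from baseline, and a score of 4 or 5 at a clinic visit reported as a serious adverse event. SAP 10.1 tabulates these by arm, and its treatment-emergent definition includes earlier conditions that became more severe or frequent. The listing shows every visit for any patient with an event. This stands in part. A reader might infer that the trial cannot report its suicidality endpoint at all, or that a move from Type 1 to Type 3 would pass unrecorded; the documents do not support either inference. But the adverse event route rests on the investigator's view of what is significant, it does not cover new Type 1 ideation, and it does not give a C-SSRS count of patients who worsened.

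A second reply is that the closing sentence of Protocol 13.5 asks only for a tabulation and listing, which SAP 10.3 provides. That is correct, and for C-SSRS the term treatment-emergent appears only in the synopsis. The protocol is therefore not uniform itself. The change-from-baseline endpoint nevertheless stands in the same Section 13.5.

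A third reply concerns size. Entry is also restricted by the MINI suicidality module, MADRS item 10 and the investigator's judgment, so it would be wrong to say that Type 4-5 ideation is the only suicidality exclusion. The share entering with Types 1-3 could be small. Randomization makes the mixing equal between arms in expectation. The tables are descriptive, and the missing ones can be built later. All of this stands and limits the weight of the point.

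**Conclusion.** The point holds as a gap between the stated endpoint and the planned tables. SAP 10.3 makes no within-patient comparison with baseline, and no planned table counts by arm the patients whose ideation was new or worse. The consequence is confined to Types 1-3 and the ideation totals, in a descriptive comparison.

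Two stronger conclusions are tempting. One is that carry-over dominates the planned count. That depends wholly on assumed rates: at the low end of Step 3, carry-over is 9.0 of 17.5 percentage points on drug, about half, and in Step 4 it can be as low as 22%. The other is that the most serious signals would be masked. They would not be, because recent Type 4-5 ideation and suicidal behavior are excluded at entry.

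The figures of 1.10-1.32 for a true 2.0 assume 15-35% with Type 1-3 ideation at entry, 60-80% of these reporting it again, no drug effect in that group, and new ideation in 5% and 10% of the rest. They show direction and plausible scale, not an estimate for this trial. The change is worth making before unblinding, chiefly because the baseline reference is a choice that should not be made with the results in view.

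**What to change.** In SAP 10.3:

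1. Define treatment-emergent ideation as a worst on-treatment type (1-5) higher than the patient's baseline type, with 0 for no ideation. Take baseline under the existing rule in SAP 7.1, the last assessment before first dose, which is Visit 2.
2. Report that count by arm, with a shift table of baseline type (0-5) by worst on-treatment type (0-5).
3. Repeat both as supportive tables, with the worst type over Screening (past 6 months) and Visit 2 as the reference. Footnote the differing recall periods. This reference should not be the only one: a patient with Type 3 ideation some months before Screening, none at Visit 2 and Type 3 again on drug would not count as emergent under it.
4. Keep the planned any-on-treatment counts. They already serve for suicidal behavior.

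The cost is one definition and a few extra descriptive tables from data already collected, with no change to conduct or sample size.

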#### **10.4 Vital Signs**

Descriptive summaries (mean, SD, median, minimum, and maximum) of actual values and changes from baseline at each assessment time point and last on-treatment assessment will be calculated for vital signs including weight, BMI, body temperature, pulse rate, systolic blood pressure and diastolic blood pressure. 95% confidence intervals will be presented for change from baseline.

These summaries will be presented by treatment and assessment time for the Safety population. ET data will be mapped to the closest visit window as described in [Section 7.1.2](#), but will typically only be used if a valid assessment was not collected then (scheduled visits will usually be closer to the target visit day and will take precedence if the ET and scheduled visit are equidistant to the target visit day).

#### **10.5 Physical Examination and Visual Examination of Oral Cavity**

A full physical examination will be performed at Screening Visit 1 only. A data listing of the physical examination results will be performed.

A visual examination of the oral cavity will be assessed at Screening, Baseline, and Week 12. A visual examination is to be done any time a participant spontaneously reports an oral adverse event (aside from AEs known to be sensory-only, such as numbness, tingling or bitter taste) to confirm presence or absence of any signs of mucosal irritation or other visible abnormalities. A data listing of the visual examination results performed at each scheduled visit and at the time of an adverse event will be presented.

#### **10.6 Electrocardiogram (ECG)**

A 12-lead ECG will be performed only at the Screening Visit. The standard ECG parameters including rhythm, heart rate, and intervals for PR, QRS, QT and QTcF (Fridericia's) correction for heart rate will be recorded. A data listing of ECG results will be provided.

#### **10.7 Assessment of Changes in Sexual Function: Changes in Sexual Functioning Questionnaire Short-Form (CSFQ-14)**

The CSFQ-14 ([Keller et al. 2006](#)) is validated scale with internal reliability designed to allow a participant to self-evaluate his or her sexual behaviors or problems in several areas. The CSFQ-14 will be administered at Baseline (Visit 2) and Week 12/ET (Visit 6). It yields a total score, three subscales corresponding to phases of the sexual response cycle (i.e. desire, arousal, orgasm), and five subscales corresponding to important

dimensions of sexual functioning. It is considered a useful scale for assessing sexual side effects of medications. For all items, higher scores reflect higher sexual functioning. For 12 of the 14 items, higher sexual functioning corresponds to greater frequency or enjoyment/pleasure (e.g. 1=never to 5 = every day). For two items (item 10, assessing loss of interest after arousal for women and priapism for men, and item 14, assessing painful orgasm), higher sexual functioning corresponds to lower frequency (e.g. 1=every day to 5=never). Items 10 and 14 are included in the total score but not in any scale score.

Descriptive summaries (mean, SD, median, minimum, and maximum) of actual values and changes from baseline at each assessment time point will be reported.

